2.8.2. Basal, Bolus and Total Exogenous Insulin

The amount of basal, bolus and total exogenous insulin will be analyzed using the Repeated Measures Analysis of Covariance model indicated in Section 2.8.1. Least squares mean, standard error and 95% confidence intervals will be presented for each treatment regimen and changes between treatment regimens.

Total daily non-oral insulin requirements in units per kilogram (kg) body weight will also be analyzed in a fashion similar to basal, bolus and total exogenous insulin.

2.8.3. Continuous Glucose Monitoring

Continuous Glucose Monitoring (CGM) will be summarized using 3 different time intervals:

- Daytime (6AM to 10PM),
- Nighttime (10PM to 6AM) and
- 24 Hour (6AM to 6AM).

The area under the curve (AUC) will be derived for each of the time periods for each of the 10 days for each treatment regimen. The average glucose measurement will be derived by dividing the AUC by the number of observed hours.

In addition to the mean values, the following CGM parameters will be derived for each time interval:

- Time that Glucose Value is Between 70 and 180,
- Time that Glucose Value is Less Than 70,
- Time that Glucose Value is Greater Than 180,

- Time that Glucose Value is Greater Than 250,
- Low Blood Glucose Index, and
- Glucose below 70 mg/dL Area Over the Curve (AOC₇₀)

All of the CGM parameters will be analyzed for each of the time periods (24-hour, daytime and nighttime) using the Repeated Measures Analysis of Covariance Model indicated in section 2.8.1.

Individual and mean figures will be generated to present the glucose curves / data for the 24-hour, daytime and nighttime measurements.

2.8.4. Other Endpoints of Interest

HbA1c, average patient reported carbohydrate intake and body weight will be summarized using an Analysis of Covariance Model as indicated in Section 2.8.1.

2.9. Interim Analyses

There are no interim analyses planned for this study.

2.10. Other Analyses

No other analyses are planned at this time.

2.11. Sample Size and Power Considerations

An estimated total of approximately 26 subjects are planned to be randomized to participate in the two dosing conditions in a randomized order. The study objectives (primary and secondary) have not been previously explored, so there are no estimates of means or standard deviations to perform power calculations.

2.12. Randomization Scheme and Codes

The randomization details for this study are presented in a separate randomization plan.

2.13. Handling Missing Data

Listings will be provided for all data. Descriptive statistics will be provided for all planned visits as provided on the electronic Case Report Forms (eCRFs).

Dates related to the adverse events and medications will be imputed using the rules below in an effort to categorize them properly into the summary tables.

Imputing partial or missing start dates:

- If the year is unknown, then the start date will not be imputed. The date will remain missing.

- If the month is unknown and the year is the same as the first dose date of the study, then impute the month and day of the date to be equal to the first dose month and day. Otherwise, impute the month as January.
- If the day is unknown and the month and year are the same as the first dose date of the study, then impute the day to be equal to the day of the first dose. Otherwise, impute the day as '01'.

Impute partial or missing stop dates:

- If the year is unknown, then the stop date will not be imputed. The date will remain missing.
- If the month is unknown, impute the month as December.
- If the day is unknown, impute the day to be the last day of the month.

If an imputed stop date is greater than the date of study completion/discontinuation date of the study, then the imputed stop date will be set equal to the date of completion/discontinuation date.

There is no plan to impute missing CGM data.

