1.2. Study Overview

This study is designed to compare ORMD-0801 given once a day (QD) versus three times a day (TID) in subjects with Type 1 Diabetes (T1D). The study will consist of seven visits (including Screening Visit).

Subjects will come in for a screening visit to determine eligibility for participation in the study. Eligible subjects will be scheduled to return to the clinic approximately 1 week later. Subjects fulfilling all inclusion/exclusion criteria will have a Continuous Glucose Monitor (CGM) placed, provided with a diary, dispensed placebo capsules and asked to return to the clinic in approximately 10 days for randomization.

At the randomization visit (Visit 3), data from the CGM will be downloaded and diaries will be collected and reviewed. Subjects will be randomized to receive either ORMD-0801 24 mg given once daily at bedtime, or ORMD-0801 8 mg given three times a day, 45-90 minutes before meals.

Subjects will be instructed to return to the clinic in eighteen days for the next visit (Day 18). On Day 18 (Visit 4), a CGM will be placed and a diary will be provided.

Subjects will return to the clinic ten days following Visit 4, on Day 28 (Visit 5). Compliance will be assessed, data from the CGM will be downloaded, the diary will be collected, and subjects will be crossed over to the alternate treatment regimen.

Subjects will be instructed to return to the clinic in 18 days for the next visit (Day 46). On Day 46 (Visit 6), a CGM will be placed and a diary will be provided.

Subjects will return to the clinic on Day 56 (Visit 7) compliance will be assessed, data from the CGM will be downloaded and diary will be collected.

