2.5. Study Drug Duration and Compliance

This is a two-period crossover study. A table summarizing the number of days on study medication, the number of tablets taken and the percent compliance (100*number of tablets taken / expected number of tablets) by treatment regimen will be presented.

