2.7. Safety Evaluations

2.7.1. Adverse Events

Adverse events will be coded using the Medical Dictionary for Drug Regulatory Affairs (MedDRA) version 21.0 and tabulated, including categorical information of interest such as onset and resolution times, time of onset relative to dose, severity at onset, maximum severity, causal relationship to study medication, and action taken.

Treatment-emergent adverse events (TEAEs) are defined as any AE that starts or increases in severity after the first randomized dose of study treatment. The incidence of TEAEs will be tabulated by MedDRA preferred term, system organ class, treatment group, severity, and assigned relationship to study treatment. Adverse events will also be summarized by severity and relationship to the investigational product (IP).

The incidence of serious AEs, drug-related AEs, serious and drug-related AEs, and any AEs resulting in discontinuation from the study will be listed.

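### SAP 2.13 imputes partial adverse-event onset dates without using the crossover date, so period-2 events can be dated into period 1 and counted under the wrong regimen

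*SAP*

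**What the plan says.** SAP 2.13 states why it imputes adverse-event and medication dates: they "will be imputed using the rules below in an effort to categorize them properly into the summary tables". The start-date rule for a missing day opens with "If the day is unknown and the month and year are the same as the first dose date of the study", and continues "then impute the day to be equal to the day of the first dose. Otherwise, impute the day as '01". The rule for a missing month opens with "If the month is unknown and the year is the same as the first dose date of the study"; the onset then takes the month and day of first dose, and otherwise the month becomes January. The date of the switch between regimens is not mentioned.

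SAP 2.5 describes the design: "This is a two-period crossover study". The switch is at Visit 5, Day 28 (SAP 1.2; protocol 3.6, window of 2 days either way). The next supply is dispensed at that visit, and protocol Table 1 shows no washout.

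SAP 2.7.1 plans the tables: "The incidence of TEAEs will be tabulated by MedDRA preferred term, system organ class, treatment group, severity, and assigned relationship to study treatment". It defines a treatment-emergent event as "any AE that starts or increases in severity after the first randomized dose of study treatment", which is again tied to first dose only. Neither document says how an event is allotted to QD or TID.

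**The concern.** A rule that separates only before from after first dose is enough in a parallel-group trial. Here each subject takes both regimens and the tables are split by treatment, so a second boundary matters. An onset in the crossover month with no day recorded is set to the start of that month or to the first-dose day. Either date usually lies in period 1, even when the event arose on the second regimen. The error has one direction in time: it adds to period 1 and takes from period 2. Safety is a secondary objective (SAP 1.3.2), and with about 26 subjects a few misplaced events can show in a sparse table.

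**Working it through.** The documents give no figure on this point, so there is none to reproduce.

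**Inputs.** The start-date rule (SAP 2.13); the switch at Day 28 and the end at Day 56, each with a window of 2 days (protocol 3.6 and 3.8).

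**Assumptions.** First-dose dates are spread evenly over the calendar, onset is uniform within a period, regimen follows the imputed start date, and the first dose of the study means the first randomized dose.

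**Example with an assumed date.** First dose 10 March is Day 1, so 1 April is Day 23 and 6 April is Day 28. An event on 20 April (Day 42) with the day missing becomes 1 April (Day 23), in period 1. With the month missing it becomes 10 March (Day 1).

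**Direction.** For any on-treatment event the imputed date is the first-dose date, the first of the onset month, or 1 January of the onset year, and never later than the true onset. A period-1 event therefore cannot move to period 2: 0%.

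**Day missing, by hand.** Take 30-day months. An onset k days after the first day of period 2 moves when the switch is not on the 1st and the onset is in the same calendar month. That holds for 29 − k of the 30 possible switch days, so the share is (29 − k)/30.
- 28-day period 2 (k = 0 to 27): (29 + 28 + ... + 2)/(28 × 30) = 434/840 = 51.7%
- First 7 days (mean k = 3): 26/30 = 86.7%
- Last 10 of 28 days (mean k = 22.5): 6.5/30 = 21.7%

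**Day missing, real calendar.** Every first-dose date in 2018 to 2020 (years chosen arbitrarily) was combined with every onset day:

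| Scenario | Period 2 to period 1 |
|---|---|
| Period 2 = Days 28-56 | 50.7% |
| Period 2 = Days 29-56 | 52.4% |
| Across the visit windows | 44.6% to 57.3% |
| Onset in first 7 days of period 2 | 87% |
| First 14 days | 75% |
| Last 14 of 28 days | 29% |
| Last 10 of 28 days | 23% |

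The reverse move was 0% in every window scenario. For a single subject the share can run from 0% to 100%, depending on where the switch falls in the month.

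**Month missing.** In the year of first dose the rule always returns the first-dose date, so 100% of period-2 events move. Over all start dates it is about 96%.

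**Effect on the QD-TID difference.** Let a and b be the true QD and TID counts of day-missing events, with half of each in period 2 (balanced sequences, no period effect), and p the share moved.
- QD as tabulated: a/2 + (1 − p)a/2 + pb/2
- TID as tabulated: b/2 + (1 − p)b/2 + pa/2
- Difference: (a − b)(1 − p)

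With p = 0.52, 48% of the difference among these events remains, with its sign unchanged.

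**Sensitivity to the meaning of first dose.** If it meant the run-in placebo dose, about 50% of day-missing period-2 events would still move, and about 54% of day-missing period-1 events would be dated before randomization.

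**The case against.** The strongest objection is that no text says the imputed date chooses the regimen. SAP 2.7.1 uses dates only to define treatment emergence, and 2.6 cites 2.13 only for prior versus concomitant medication; both need first dose alone. SAP 2.7.1 speaks of treatment group where 2.5 and 2.7.2 to 2.7.4 speak of regimen. The table shells are in a separate file and could settle the matter. This stands in part: a reader might infer that the SAP credits events to the wrong regimen by an explicit rule, and the documents do not go that far. They do say that the dates are imputed in order to categorize events into tables, and those tables are by treatment. The inference is well supported, but it remains an inference.

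Second, one half is an average that depends on uniform onset. This stands, and the range of 23% to 87% belongs with it.

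Third, few events will be touched. Visits are at most about 18 days apart, onset date is a listed eCRF item (protocol 7.4.1), omissions are queried (protocol 9.2), and hypoglycemia is reported by regimen from its own log (SAP 2.7.2). If there were 26 to 52 period-2 events with 1 to 5% lacking a day (assumed figures), the rule would move between 26 × 0.01 × 0.52 = 0.1 and 52 × 0.05 × 0.52 = 1.4 events in the whole trial. An unknown month is less likely still. The tables are descriptive and count subjects, so a moved event may not change a cell. All of this stands and limits the importance of the point. It does not make the rule suit a crossover.

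**Conclusion.** The rule is wrong for this design as written, with low impact. If the imputed onset date feeds the by-treatment tables, about 51 to 52% of day-missing period-2 events are placed in period 1, and no period-1 event is placed in period 2. The percentage rests on uniform onset and evenly spread start dates; the one-way direction does not.

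Two stronger readings are not supported. The figure is not half of all period-2 adverse events: it applies only to those with a missing day, whose number the documents do not give and which is probably small. Nor does the one-way shift in time favour QD or TID. With balanced sequences it moves TID events to QD in one sequence and QD events to TID in the other, which blurs the comparison. Balance is itself an assumption, because SAP 2.12 leaves the scheme to a separate randomization plan. No primary or secondary efficacy analysis is affected.

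**What to change.** Two additions to the SAP:

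- In 2.7.1, state that each treatment-emergent event is assigned to the regimen in use at its onset.
- In 2.13, state that when the known parts of an onset date fit both periods, the period is taken from the visit at which the event was first recorded. Visit 4 or 5 means period 1. Visit 6 or 7 means period 2, with the imputed date no earlier than the first period-2 dose, unless the stop date or other recorded information shows onset before the switch.

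Imputing to the crossover date whenever the month matches would not do. It brings the move from period 2 to period 1 down to 0%, but sends 54% of day-missing period-1 events into period 2. Month and year alone cannot settle the period, so a further item of information is needed.

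The cost is a little SAP text and some programming. There are two small downsides. The recording visit is not among the adverse-event fields listed in protocol 7.4.1, so the sponsor should confirm that it can be retrieved from the eCRF or source. And a period-1 event first reported at Visit 6 would be placed in period 2 unless other information corrects it.

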2.14. Protocol Deviations

Protocol deviations will be displayed in a data listing as provided by the clinical team.

2.15. Computer Systems and Packages Used for Statistical Analyses

Server SAS® version 9.4 on the Microsoft Windows Server 2008R2 64-bit platform will be used for all analyses. All computations will be performed using SAS®. The exact form of the various algorithms will be the SAS® defaults. The output from any SAS® procedure will be used in the tables using SAS® macros.

3. Data Listing Shells

3.1. Data Listings Table of Contents

The following post-text listings will be generated.

| | |
|------------|---|
| 16.1.7 | Randomization Schedule |
| 16.2.1 | Subject Completion/Discontinuation |
| 16.2.2 | Protocol Deviations |
| 16.2.3 | Population Status |
| 16.2.4.1 | Demographics and Baseline Characteristics |
| 16.2.4.2 | Childbearing Status |
| 16.2.4.3 | Inclusion / Exclusion Criteria and Informed Consent |
| 16.2.4.4 | Medical History |
| 16.2.4.5.1 | Prior and Concomitant Medications |
| 16.2.4.5.2 | Non-Drug Treatment |
| 16.2.5.1 | Study Drug Accountability |
| 16.2.5.2 | Study Drug Dosing Time – Final 10 Days of Treatment |
| 16.2.6.1 | Exogenous Insulin Usage – Final 10 Days of Treatment |
| 16.2.6.2.1 | Continuous Glucose Monitoring – Daytime Parameters |
| 16.2.6.2.2 | Continuous Glucose Monitoring – Nighttime Parameters |
| 16.2.6.2.3 | Continuous Glucose Monitoring – 24 Hour Parameters |
| 16.2.6.4 | Carbohydrate Intake – Final 10 Days of Treatment |
| 16.2.6.5 | HbA1c Values |
| 16.2.6.6 | Weight Values |
| 16.2.7.1.1 | Adverse Events |
| 16.2.7.1.2 | Serious Adverse Events |
| 16.2.7.1.3 | Adverse Events Leading to Study Treatment Discontinuation |
| 16.2.7.2 | Hypoglycemic / Hyperglycemic Log |
| 16.2.8.1 | Laboratory Test Results - Chemistry |
| 16.2.8.2 | Laboratory Test Results - Hematology |
| 16.2.8.3 | Laboratory Test Results – Urinalysis |
| 16.2.9.1 | Vital Signs |
| 16.2.9.2 | Electrocardiogram Results |

| | |
|----------|------------------------------|
| 16.2.9.3 | Physical Examination Results |
|----------|------------------------------|

3.2. Data Listings

All subjects and all data will be presented in the listings. The listings will be sorted by treatment and subject number.

There are currently 29 listings that are planned to be generated. The 29 listings are broken down as follows: 16 Standard Unique, 4 Standard Repeat, 9 Non-Standard Unique and 0 Non-Standard Repeat.

4. Summary Table and Figure Shells

4.1. Post-text Table of Contents

The following post-text tables will be generated.

| Table Number | Table title |
|--------------|--|
| 14.1.1 | Summary of Subject Disposition (Safety Population) |
| 14.1.2 | Summary of Demographics and Baseline Characteristics (Safety Population) |
| 14.1.3 | Summary of Medical History (Safety Population) |
| 14.1.4.1 | Summary of Prior Medications (Safety Population) |
| 14.1.4.2 | Summary of Concomitant Medications (Safety Population) |
| 14.1.5 | Summary of Study Medication Compliance (Safety Population) |
| 14.2.1 | Summary of Exogenous Insulin Usage (Safety Population) |
| 14.2.2.1 | Summary of Continuous Glucose Measurement Parameters – Daytime (Safety Population) |
| 14.2.2.2 | Summary of Continuous Glucose Measurement Parameters – Nighttime (Safety Population) |
| 14.2.2.3 | Summary of Continuous Glucose Measurement Parameters – 24-Hour (Safety Population) |
| 14.2.3 | Summary of Carbohydrate Intake (Safety Population) |
| 14.2.4 | Summary of HbA1c (Safety Population) |
| 14.2.5 | Summary of Weight (Safety Population) |
| 14.3.1.1 | Adverse Events Overall Summary (Safety Population) |

| Table Number | Table title |
|--------------|---|
| 14.3.1.2 | Summary of Treatment Emergent Adverse Events by System Organ Class, and Preferred Term (Safety Population) |
| 14.3.1.3 | Summary of Treatment Emergent Adverse Events Leading to Discontinuation of Study (Safety Population) |
| 14.3.1.4 | Summary of Serious Treatment Emergent Adverse Events (Safety Population) |
| 14.3.1.5 | Summary of Treatment Emergent Adverse Events by System Organ Class, Preferred Term, and Severity (Safety Population) |
| 14.3.1.6 | Summary of Treatment Emergent Adverse Events by System Organ Class, Preferred Term, and Relationship to Study Treatment (Safety Population) |
| 14.3.2.1 | Summary of Laboratory Values – Chemistry (Safety Population) |
| 14.3.2.2 | Summary of Laboratory Values – Hematology (Safety Population) |
| 14.3.2.3 | Summary of Laboratory Values – Urinalysis (Safety Population) |
| 14.3.3 | Summary of Vital Signs (Safety Population) |
| 14.3.4 | Summary of Hypoglycemic Events (Safety Population) |
| 14.3.5 | Summary of Physical Examination Findings (Safety Population) |

4.2. Summary Tables

There are currently 25 tables that are planned to be generated. The 25 tables are broken down as follows: 9 Standard Unique, 4 Standard Repeat, 12 Non-Standard Unique and 0 Non-Standard Repeat.

4.3. Post-text Figures Tables of Contents

The following post-text figures will be generated.

| Figure Number | Figure Title |
|---------------|---|
| 14.2.1.1.1 | Exogenous Insulin Usage - Basal – Individual Observed Values |
| 14.2.1.1.2 | Exogenous Insulin Usage - Basal – Mean Observed Values |
| 14.2.1.2.1 | Exogenous Insulin Usage - Bolus – Individual Observed Values |
| 14.2.1.2.2 | Exogenous Insulin Usage - Bolus – Mean Observed Values |
| 14.2.1.3.1 | Exogenous Insulin Usage - Total – Individual Observed Values |
| 14.2.1.3.2 | Exogenous Insulin Usage - Total – Mean Observed Values |
| 14.2.2.1.1 | Continuous Glucose Measurements - Individual Observed Values – 24-Hours |
| 14.2.2.1.2 | Continuous Glucose Measurements - Mean Observed Values – 24-Hours |

| Figure Number | Figure Title |
|---------------|--|
| 14.2.2.2.1 | Continuous Glucose Measurements - Individual Observed Values – Daytime |
| 14.2.2.2.2 | Continuous Glucose Measurements - Mean Observed Values – Daytime |
| 14.2.2.3.1 | Continuous Glucose Measurements - Individual Observed Values – Nighttime |
| 14.2.2.3.2 | Continuous Glucose Measurements - Mean Observed Values – Nighttime |

4.4. Post-Text Figures

There are currently 12 figures that are planned to be generated. The 12 figures are broken down as follows: 0 Standard Unique, 0 Standard Repeat, 8 Non-Standard Unique and 4 Non-Standard Repeat.

4.5. Table Shells

The table shells can be found in a separate file. The following number of decimal places will be used when presenting summary statistics:

- N to 0 decimal places
- Minimum and maximum to the same number of decimal places as recorded in the raw data.
- Means and medians to 1 more decimal place than is recorded in the raw data. Standard deviations to 2 more decimal places than is recorded in the raw data.
- Percentages to 1 decimal place.

The precision may be changed for individual endpoints as needed.
